6.12.4. Clinical Laboratory Evaluation

Clinical laboratory assessments include hematology, serum chemistry, urinalysis, and safety-related immune markers such as neutrophil counts. All laboratory tests will be presented using the international system of unit (SI).

Continuous laboratory tests will be summarized as changes from baseline to last observation for patients who have both baseline and at least 1 postbaseline result for Periods 2 and 3:

- The scheduled visits/measurements will be included. The unscheduled visits and the repeat measurements will be excluded.
- For Safety Population during Period 2 and Maintenance Dosing Period Primary Population during Period 3, treatment group comparisons will be conducted using an ANCOVA model with treatment group and baseline value in the model.
- Data will be analyzed based on original scale.

Laboratory test observed values at each visit (starting at baseline) and change from baseline to each scheduled visit, respectively, will be displayed in box plots for patients who have both a baseline and at least one postbaseline result for Periods 2 and 3. These box plots will be used to evaluate trends over time and to assess a potential impact of outliers on central tendency summaries.

- The scheduled visits/measurements will be included. The unscheduled visits and the repeat measurements will be excluded.
- The following summary statistics will be included as a table below the box plot: number of patients with a baseline and at least one postbaseline result, mean, standard deviation, minimum, Q1, median, Q3, and maximum.
- Data will be summarized based on original scale.
- On the box plots of the laboratory test observed values, the lines of the reference ranges/limits (by using the performing laboratory reference ranges) will be added. In cases where limits vary across age and gender, the lowest of the high limits and the highest of the low limits will be used.

The number and percentage of patients with a treatment-emergent or follow-up emergent abnormal, high, or low for laboratory tests will be summarized by treatment group for each study period. The comparisons between and among treatment groups will be conducted using Fisher's exact test for the Safety Population for Period 2 and Maintenance Dosing Period Primary Population for Period 3.

- All scheduled, unscheduled and repeated measurements will be included.
- Performing laboratory will be used to define the low and high limits reference ranges except leukocyte, neutrophil, lymphocyte and platelet counts, where Lilly defined lower limit of normal will be used for these 4 labs.
- Alanine aminotransferase (ALT), aspartate aminotransferase (AST), total bilirubin, alkaline phosphatase (ALP), neutrophils, leukocytes, platelets, and lymphocytes will not be included in the treatment-emergent abnormal, high, or low summary as a separate

analysis addressing the risk of liver injury is described in Section 6.12.3.1 and a separate analysis addressing Leukocytes (WBC) and Platelets is described in Section 6.12.4.1.

- Note that the ranges are defined by a lower limit of normal (LLN) and an upper limit of normal (ULN). A result that is greater than or equal to the LLN and less than or equal to the ULN is considered to be within the normal ranges.
- For categorical laboratory tests:
 - Treatment-emergent **abnormal** value is defined as a change from normal at all baseline visits to abnormal at any time postbaseline during the treatment period.
 - Follow-up emergent **abnormal** result is defined as a change from normal at baseline to abnormal at any time during the follow-up period.
- For continuous laboratory tests:
 - Treatment-emergent **high** value is defined as a change from a value less than or equal to the ULN at all baseline visits to a value greater than the ULN at any time postbaseline during the treatment period.
 - Treatment-emergent **low** value is defined as a change from a value greater than or equal to the LLN at all baseline visits to a value less than the LLN at any time postbaseline during the treatment period.
 - Follow-up emergent **high** value is defined as a change from a value less than or equal to the ULN at baseline to a value greater than the ULN at any time postbaseline during the follow-up period.
 - Follow-up emergent **low** value is defined as a change from a value greater than or equal to the LLN at baseline to a value less than the LLN at any time postbaseline during the follow-up period.

By-patient listing of abnormal laboratory test results (criteria defined in the shift tables excluding the normal category) for parameters of special interest (hepatic, leukocytes and platelets) will be provided.

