#### **10.3.2.6. Safety-Related Immune Markers**

IL-17 is believed to play a role in neutrophil homeostasis and in neutrophil-dependent host defense against extracellular infections (Happel et al. 2003; Huang et al. 2004; Milner et al. 2008). Neutrophil counts will therefore serve as a safety marker in the current investigation.

Ixekizumab is not expected to affect the numbers of B, T, and natural killer (NK) lymphocytes or serum immunoglobulin subclasses A, G, and M (IgA, IgG, and immunoglobulin M [IgM], respectively) in peripheral blood. However, since this is a novel immunomodulatory drug, these parameters will be measured in patients.

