#### **12.2.8.2. Clinical Laboratory Tests**

Laboratory assessments will be presented as mean changes from baseline to last observation, change from baseline to minimum postbaseline value, change from baseline to maximum postbaseline value and as incidence of treatment-emergent abnormal, high, or low laboratory values. Shift tables will be presented for selected parameters.

- Treatment-emergent **abnormal** value = a change from normal at all baseline visits to abnormal at any time postbaseline.
- Treatment-emergent **high** value = a change from a value less than or equal to the high limit at all baseline visits to a value greater than the high limit at any time postbaseline.
- Treatment-emergent **low** value = a change from a value greater than or equal to the low limit at all baseline visits to a value less than the low limit at any time postbaseline.

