6.12.4.1. Leukocytes (WBC) and Platelets

Further analyses will be conducted for total leukocytes, neutrophils, platelets, lymphocytes, monocytes, eosinophils, and basophils. Unless otherwise specified, neutrophils will be summarized as absolute neutrophils (derived by adding segmented neutrophils and band neutrophils).

Shift table will be produced showing the number and percentage of patients shifting from baseline to a minimum postbaseline result in each relevant category by treatment groups for Periods 2 and 3, respectively:

- Scheduled visits, unscheduled visits, and repeat measurements will be included.
- Baseline is defined as the minimum result during the defined baseline period or baseline.
- Use the minimum non-missing postbaseline value within each study period.
- The parameters and categories are:
 - Leukocytes: $\geq 1 \times \text{LLN}$ (Normal), $< \text{LLN}$ to $\geq 3.0 \times 10^9/\text{L}$ (Grade 1), $< 3.0 \times 10^9/\text{L}$ to $\geq 2.0 \times 10^9/\text{L}$ (Grade 2), $< 2.0 \times 10^9/\text{L}$ to $\geq 1.0 \times 10^9/\text{L}$ (Grade 3), and $< 1.0 \times 10^9/\text{L}$ (Grade 4).

- Neutrophils: $\geq 1 \times \text{LLN}$ (Normal), $< \text{LLN}$ to $\geq 1.5 \times 10^9/\text{L}$ (Grade 1), $< 1.5 \times 10^9/\text{L}$ to $\geq 1.0 \times 10^9/\text{L}$ (Grade 2), $< 1.0 \times 10^9/\text{L}$ to $\geq 0.5 \times 10^9/\text{L}$ (Grade 3), and $< 0.5 \times 10^9/\text{L}$ (Grade 4)
- Platelets: $\geq 1 \times \text{LLN}$ (Normal), $< \text{LLN}$ to $\geq 75.0 \times 10^9/\text{L}$ (Grade 1), $< 75.0 \times 10^9/\text{L}$ to $\geq 50.0 \times 10^9/\text{L}$ (Grade 2), $< 50.0 \times 10^9/\text{L}$ to $\geq 25.0 \times 10^9/\text{L}$ (Grade 3), and $< 25.0 \times 10^9/\text{L}$ (Grade 4).
- Lymphocytes: $\geq 1 \times \text{LLN}$ (Normal), $< \text{LLN}$ to $\geq 0.8 \times 10^9/\text{L}$ (Grade 1), $< 0.8 \times 10^9/\text{L}$ to $\geq 0.5 \times 10^9/\text{L}$ (Grade 2), $< 0.5 \times 10^9/\text{L}$ to $\geq 0.2 \times 10^9/\text{L}$ (Grade 3), and $< 0.2 \times 10^9/\text{L}$ (Grade 4).
- The above LLNs are defined as:
 - Leukocytes: $\text{LLN} = 4.0 \times 10^9/\text{L}$
 - Neutrophils: $\text{LLN} = 2.0 \times 10^9/\text{L}$
 - Platelets: $\text{LLN} = 150 \times 10^9/\text{L}$
 - Lymphocytes: $\text{LLN} = 1.1 \times 10^9/\text{L}$
- With additional categories:
 - Decreased; postbaseline category $<$ baseline category
 - Increased; postbaseline category $>$ baseline category

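### SAP 6.12.4 removes four blood counts from the Fisher-tested treatment-emergent summary in Periods 2 and 3, and the section cited as the replacement names no test and cannot show a rise

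*SAP*

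**What the plan says.** SAP 6.12.4 sets up the summary: "The number and percentage of patients with a treatment-emergent or follow-up emergent abnormal, high, or low for laboratory tests will be summarized" by treatment group and study period. The test follows: "The comparisons between and among treatment groups will be conducted using Fisher's exact test for the Safety Population for Period 2" and, for Period 3, the Maintenance Dosing Period Primary Population.

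Two adjacent bullets then give rules for that summary. The first takes reference limits from the performing laboratory, except for leukocytes, neutrophils, lymphocytes and platelets, "where Lilly defined lower limit of normal will be used for these 4 labs". The second says that, along with ALT, AST, total bilirubin and ALP, "neutrophils, leukocytes, platelets, and lymphocytes will not be included in the treatment-emergent abnormal, high, or low summary". The reason given for the blood counts is that "a separate analysis addressing Leukocytes (WBC) and Platelets is described in Section 6.12.4.1".

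SAP 6.12.4.1 provides a table of patients "shifting from baseline to a minimum postbaseline result in each relevant category by treatment groups", with grades below the sponsor limits, and a box plot of change from minimum baseline to minimum postbaseline value.

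Protocol 12.2.8.2 plans to present laboratory results, among other ways, "as incidence of treatment-emergent abnormal, high, or low laboratory values", and excepts no analyte. Protocol 10.3.2.6 says: "Neutrophil counts will therefore serve as a safety marker in the current investigation".

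**The concern.** For Periods 2 and 3 the two bullets do not fit together: one sets a limit for four counts in a summary, and the other takes those counts out. A programmer would follow the exclusion. The replacement then has to deliver what was removed, namely a count of emergent lows, a count of emergent highs, and a between-arm comparison of each. It clearly delivers only the first.

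Neutrophils are the protocol's named safety marker and cytopenias are an adverse event of special interest. Monocytes, eosinophils and basophils are not on the exclusion list, so they keep an explicitly tested high/low row while neutrophils lose theirs. The high side of all four counts also drops out of the incidence tables, with no reason given for departing from the protocol.

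**Working it through.** The plan states no figure on this point, so the check is a comparison of rules, with illustrative patients run through the shift-table rule.

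**1. Low side.** Under SAP 6.12.4, a treatment-emergent low is a value at or above the lower limit at all baseline visits and below it at any time postbaseline. That is the same as: minimum baseline ≥ LLN and minimum postbaseline < LLN. SAP 6.12.4.1 uses the minimum baseline value, the minimum postbaseline value, and scheduled, unscheduled and repeat measurements. Its LLNs are 4.0 (leukocytes), 2.0 (neutrophils), 1.1 (lymphocytes) and 150 (platelets), all ×10⁹/L. Where both rules use the same baseline visits, a shift from Normal to any of Grades 1 to 4 is a treatment-emergent low. Example with assumed values: neutrophils 4 at baseline, then 2.5, 1.4 and 3. The minimum is 1.4, which is below 1.5 and at least 1.0, so the patient moves from Normal to Grade 2. Emergent lows are counted by arm.

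**2. High side.** The top category in SAP 6.12.4.1 is Normal, defined only as ≥ LLN. Assumed patients who rise and fall back (×10⁹/L):

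| Count | Baseline | Postbaseline | Minimum postbaseline | LLN | Shift |
|---|---|---|---|---|---|
| Leukocytes | 8 | 9, 16, 9 | 9 | 4.0 | Normal to Normal |
| Neutrophils | 4 | 5, 12, 5 | 5 | 2.0 | Normal to Normal |
| Platelets | 250 | 300, 600, 280 | 280 | 150 | Normal to Normal |
| Lymphocytes | 2 | 2.5, 6, 2.1 | 2.1 | 1.1 | Normal to Normal |

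Every rise is classed as no change. The by-patient listing of abnormal results uses the same shift categories without Normal, so for these counts it is also low-side only.

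**3. Test.** SAP 6.12.4.1 names none. SAP 6.1.2 (Period 2) and 6.1.3.1 (Period 3) apply Fisher's exact test to other categorical safety or categorical data in general. Table RHBH.6.8 shows how the SAP treats the liver tests removed by the same sentence: hepatic elevations are marked for Fisher's exact test in Periods 2 and 3, while hepatic shifts are marked only as a summary. By that convention a shift table is descriptive. The general rule and the convention point in different directions, and the text does not settle which governs SAP 6.12.4.1.

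**4. Scope.** The summary covers treatment-emergent and follow-up-emergent results, but the exclusion names only the treatment-emergent one. The four counts therefore stay in the Period 4 follow-up-emergent rows. What is affected is 4 counts × 2 periods = 8 analyte-by-period high rows with no incidence, and 8 low rows counted but with no test stated.

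**The case against.** The strongest reply is that the exclusion is deliberate, reasoned and cross-referenced, and that the replacement is better on the low side, which is the direction of the documents' stated concern about neutrophils. Much of this stands. The same low-count patients appear by arm, with severity added. The sponsor limits are not idle: SAP 6.12.4.1 uses them, and the follow-up-emergent summary can.

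Three stronger readings are tempting, and the documents do not support them.

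- A reader might infer that high counts are reported nowhere. SAP 6.12.4 plans box plots of observed values with reference-limit lines and a table giving the maximum, and does not exclude these counts. But box plots do not count patients with an emergent high, and they omit unscheduled and repeat measurements.
- A reader might infer that low counts are never compared. Leukopenia and thrombocytopenia adverse events are Fisher-tested (Table RHBH.6.8), and change to last observation is compared by ANCOVA. But the first rests on reported terms rather than laboratory values. The second can miss a transient nadir and omits unscheduled and repeat measurements, although Protocol 10.3.3.1 allows neutrophil rechecks at unscheduled visits.
- A reader might infer that Period 4 is affected. It is not, and neutrophils have their own recovery analysis there (SAP 6.12.4.2).

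It is also fair that Protocol 12.2.1.1 says only that Fisher's test may be used for Period 2 categorical safety data, and that Protocol 12.2.1 leaves details to the SAP and lets lesser changes be justified in the study report. So no promised Period 2 test is broken. Neither provision, however, explains why the high-side incidence listed in Protocol 12.2.8.2 is dropped.

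Finally, SAP 6.12.3.1 lets a program-level safety analysis plan override it on special safety topics, which include cytopenias. That plan is not among the documents and might fill the gap.

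**Conclusion.** The point holds in a limited form, as a minor matter. In Periods 2 and 3, following SAP 6.12.4 as written drops the incidence of treatment-emergent high values for leukocytes, neutrophils, lymphocytes and platelets, contrary to Protocol 12.2.8.2. It also leaves unclear whether emergent lows, which are counted by arm, are compared between arms. The adjacent bullets on the lower limit and the exclusion conflict for the treatment-emergent summary.

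The conclusion rests on the text of the two documents and on reading shift tables as descriptive, as Table RHBH.6.8 does. If the general Fisher rule was meant to reach SAP 6.12.4.1, only the high-side gap and the unclear wording remain. The documents give no expected incidence of abnormal counts, so no power figure is attached. The comparison is an unadjusted safety test, and the efficacy conclusions are untouched.

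**What to change.** In SAP 6.12.4, limit the exclusion bullet to ALT, AST, total bilirubin and ALP, and delete the clause that cites Section 6.12.4.1 as the replacement. Keep the four counts in the treatment-emergent summary, with:

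- low defined by the sponsor limits: 4.0 for leukocytes, 2.0 for neutrophils, 1.1 for lymphocytes and 150 for platelets (×10⁹/L);
- high defined by the performing laboratory's upper limit, stated explicitly because the current bullet supplies only a lower limit for these counts;
- Fisher's exact test, as for the other analytes.

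Retain the graded shift tables and box plots in SAP 6.12.4.1. The cost is one edited sentence and a few table rows. The only downside is overlap with the shift tables on the low side.

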6.12.4.1. Leukocytes (WBC) and Platelets

Further analyses will be conducted for total leukocytes, neutrophils, platelets, lymphocytes, monocytes, eosinophils, and basophils. Unless otherwise specified, neutrophils will be summarized as absolute neutrophils (derived by adding segmented neutrophils and band neutrophils).

Shift table will be produced showing the number and percentage of patients shifting from baseline to a minimum postbaseline result in each relevant category by treatment groups for Periods 2 and 3, respectively:

- Scheduled visits, unscheduled visits, and repeat measurements will be included.
- Baseline is defined as the minimum result during the defined baseline period or baseline.
- Use the minimum non-missing postbaseline value within each study period.
- The parameters and categories are:
 - Leukocytes: $\geq 1 \times \text{LLN}$ (Normal), $< \text{LLN}$ to $\geq 3.0 \times 10^9/\text{L}$ (Grade 1), $< 3.0 \times 10^9/\text{L}$ to $\geq 2.0 \times 10^9/\text{L}$ (Grade 2), $< 2.0 \times 10^9/\text{L}$ to $\geq 1.0 \times 10^9/\text{L}$ (Grade 3), and $< 1.0 \times 10^9/\text{L}$ (Grade 4).

- Neutrophils: $\geq 1 \times \text{LLN}$ (Normal), $< \text{LLN}$ to $\geq 1.5 \times 10^9/\text{L}$ (Grade 1), $< 1.5 \times 10^9/\text{L}$ to $\geq 1.0 \times 10^9/\text{L}$ (Grade 2), $< 1.0 \times 10^9/\text{L}$ to $\geq 0.5 \times 10^9/\text{L}$ (Grade 3), and $< 0.5 \times 10^9/\text{L}$ (Grade 4)
- Platelets: $\geq 1 \times \text{LLN}$ (Normal), $< \text{LLN}$ to $\geq 75.0 \times 10^9/\text{L}$ (Grade 1), $< 75.0 \times 10^9/\text{L}$ to $\geq 50.0 \times 10^9/\text{L}$ (Grade 2), $< 50.0 \times 10^9/\text{L}$ to $\geq 25.0 \times 10^9/\text{L}$ (Grade 3), and $< 25.0 \times 10^9/\text{L}$ (Grade 4).
- Lymphocytes: $\geq 1 \times \text{LLN}$ (Normal), $< \text{LLN}$ to $\geq 0.8 \times 10^9/\text{L}$ (Grade 1), $< 0.8 \times 10^9/\text{L}$ to $\geq 0.5 \times 10^9/\text{L}$ (Grade 2), $< 0.5 \times 10^9/\text{L}$ to $\geq 0.2 \times 10^9/\text{L}$ (Grade 3), and $< 0.2 \times 10^9/\text{L}$ (Grade 4).
- The above LLNs are defined as:
 - Leukocytes: $\text{LLN} = 4.0 \times 10^9/\text{L}$
 - Neutrophils: $\text{LLN} = 2.0 \times 10^9/\text{L}$
 - Platelets: $\text{LLN} = 150 \times 10^9/\text{L}$
 - Lymphocytes: $\text{LLN} = 1.1 \times 10^9/\text{L}$
- With additional categories:
 - Decreased; postbaseline category $<$ baseline category
 - Increased; postbaseline category $>$ baseline category
 - Same; postbaseline category $=$ baseline category.

The change from minimum baseline to minimum postbaseline result for each of these leukocytes and platelets will be summarized graphically using a box plot for Periods 2 and 3, respectively.

6.12.4.2. Neutrophil Follow-Up

Neutrophil counts will be followed throughout the study. Patients will continue in Period 4 until their neutrophil counts have recovered.

The neutrophil follow-up analysis will be conducted on the Neutrophil Follow-Up Population defined as patients who have an absolute neutrophil count < 1500 cells/ μL (SI units: $< 1.5 \times 10^9/\text{L}$) at the last scheduled visit or ETV prior to entering Period 4 and less than the patient's baseline absolute neutrophil count (that is, prior to first injection at Week 0). These patients are monitored during Period 4 until neutrophil recovery.

Neutrophil clinical recovery is defined as an absolute neutrophil count ≥ 1500 cells/ μL (SI units: $\geq 1.5 \times 10^9/\text{L}$) or greater than or equal to a patient's minimum absolute neutrophil count prior to first study drug injection at Week 0.

If a patient's neutrophil count has not recovered, within 12 weeks after entering the follow-up period (Visit 802), the patient will return for Visit 803 (12 weeks after Visit 802). Additional visits may be required for appropriate patient management depending upon the degree of neutropenia. If at Visit 802, a patient has met the criteria for neutrophil recovery, the patient's participation in the study will be considered complete unless the investigator deems additional follow-up may be necessary.

The number and percentage of patients achieving neutrophil clinical recovery will be presented by treatment groups and week interval for the Neutrophil Follow-Up Population for Period 4. The number and percentage of patients with an absolute neutrophil cell count that is at least 25%,

50%, 75%, or 100% of the patient's baseline absolute neutrophil count (that is, prior to first injection at Week 0), irrespective of absolute neutrophil minimum, will be included in the summary.

6.12.5. Vital Signs and Other Physical Findings

Analyses will be conducted on vital signs and physical characteristics including systolic blood pressure (mmHg), diastolic blood pressure (mmHg), pulse (bpm), weight (kg) and BMI (kg/m²). By-patient listing of vital signs and physical characteristics will be provided.

Change from baseline to last observation for vital signs and physical characteristics will be summarized for patients who have both baseline and at least one post-baseline result, for Periods 2 and 3, respectively:

- The scheduled visits/measurements will be included. The unscheduled visits and the repeat measurements will be excluded.
- For Safety Population in Period 2 and Maintenance Dosing Period Primary Population in Period 3, treatment comparisons between and among treatment groups will be conducted using an ANCOVA with treatment group and baseline value in the model.
- Data will be analyzed based on original scale.

For vital signs and physical characteristics, the observed values at each visit (starting at baseline) and change from baseline to each scheduled visit, respectively, will be displayed in box plots for patients who have both a baseline and at least one post-baseline result. These box plots will be used to evaluate trends over time and to assess a potential impact of outliers on central tendency summaries.

- The scheduled visits/measurements will be included. The unscheduled visits and the repeat measurements will be excluded.
- The following summary statistics will be included as a table below the box plot: number of patients with a baseline and at least one post-baseline result, mean, SD, minimum, Q1, median, Q3, and maximum.
- Data will be summarized based on original scale.

To assess the effect of administration of study drug on vital signs (blood pressures and pulse rate) among patients, at Week 0 and Week 12, vital signs will be measured before the first injection and 1 hour after the injection. The box plots will be produced for pre-dose and post-dose vital signs at Week 0 (Visit 2) and Week 12 (Visit 7).

The number and percentage of patients with treatment-emergent or follow-up emergent high or low vital sign and weight at any time for Periods 2, 3 and Period 4, respectively, will be summarized.

- [Table RHBH. 6.9](#) defines the high and low baseline values as well as the limits that are specified as treatment-emergent and follow-up emergent. Note that weight does not have an abnormal baseline; therefore, the treatment-emergent and follow-up emergent values are determined by change from baseline.

- All post-baseline scheduled, unscheduled and repeated measurements will be included.
- To assess increases, change from the maximum value during the baseline period or baseline to the maximum value during each study period will be used.
- To assess decreases, change from the minimum value during the baseline period or baseline to the minimum value during each study period will be used.
- For treatment-emergent high and low:
 - A treatment-emergent **high** result is defined as a change from a value less than or equal to the high limit at baseline to a value greater than the high limit at any time that meets the specified change criteria during the treatment period.
 - A treatment-emergent **low** result is defined as a change from a value greater than or equal to the low limit at baseline to a value less than the low limit at any time that meets the specified change criteria during the treatment period.
- For follow-up emergent high and low:
 - A follow-up emergent **high** result is defined as a change from a value less than or equal to the high limit at baseline to a value greater than the high limit at any time that meets the specified change criteria during the follow-up period.
 - A follow-up emergent **low** result is defined as a change from a value greater than or equal to the low limit at baseline to a value less than the low limit at any time that meets the specified change criteria during the follow-up period.

Table RHBH. 6.9. Categorical Criteria for Abnormal Treatment-Emergent Blood Pressures and Pulse Measurement, and Categorical Criteria for Weight Changes for Adults

Parameter	Low	High
Systolic BP (mm Hg) ^a (supine or sitting – forearm at heart level)	≤90 and decrease from baseline ≥20	≥140 and increase from baseline ≥20
Diastolic BP (mm Hg) ^a (supine or sitting – forearm at heart level)	≤50 and decrease from baseline ≥10	≥90 and increase from baseline ≥10
Pulse (bpm) ^a (supine or sitting)	<50 and decrease from baseline ≥15	>100 and increase from baseline ≥15
Weight (kg)	(Loss) decrease from baseline ≥7%	(Gain) increase from baseline ≥7%

Abbreviations: BP = blood pressure; bpm = beats per minute; kg = kilogram; mm Hg = millimeters of mercury.
^a Baseline abnormal values are defined by the value presented.

